### **Other analysis supporting the tertiary analysis (including sensitivity analyses)**

A repeated measures sensitivity analysis will be conducted for endpoints measured at multiple time points using multivariable mixed-effects regression models. All available data from all participants will be included with missing values intrinsically imputed within the model rather than requiring multiple imputations. Treatment, stratification factors and time point (time since randomisation) will be entered into the model as fixed effects and the model will contain a patient specific random intercept. An interaction between time point and treatment group will be fitted as a fixed effect to allow estimation of treatment effect at each time point. We will also assess whether time should be included in the model as a random slope and different covariance structures will be explored to determine which model best fits the data.

## ***11. Safety analyses***

Binary safety variables such as self-harm, death, harm to others or being a victim of crime will be analysed in the same way as the primary outcome using log-binomial regression.

Counts of safety variables (such as number of self-harm episodes, number of times a victim of crime, etc.) will be analysed as per secondary count outcomes using Poisson or negative binomial regression models. Cause of death will be tabulated descriptively by treatment group.

## ***12. Sub-group analyses***

Sub-group analyses will be conducted for the primary endpoint to test the hypothesis that the treatment effect differs according to factors measured at baseline. The subgroup analysis will involve fitting the same model as described for the primary outcome with the inclusion of an additional interaction effect for the interaction between treatment group and the relevant subgroup variable. The p value for the interaction test will be the p-value of interest as this is the test of the stated hypothesis. The significance of the treatment variable within each subgroup separately will not be considered of interest.

## ***13. Analysis of exploratory objectives***

### **Predictors of readmission**

A risk prediction model for readmission will be developed after a more thorough literature search in order to review other potentially available models.

### **Mediator effects**

The mediator effect of contact with service (rate of contact and type of contact) will be assessed for the primary outcome (readmission to psychiatry hospital) and the secondary outcomes 1) number of nights in psychiatric hospitalization; 2) number of nights to first readmission; and 3) number of readmissions, from INDEX to 365 days.

This analysis aims to explain how the difference of treatment between the two groups occurred based on the contact with service experienced.

This analysis will consist of fitting the same models as described for the primary outcome and secondary outcomes adding each contact with service variable independently as a fixed factor. Results will report the treatment effect after this adjustment, together with 95% confidence intervals whenever possible.

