## **Mediation analysis**

To explore the effect on readmission of process variables such as rate of contact and type of contact (i.e face-to-face vs. telephone contact).

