### **Derived and computed variables**

Total scores for the following instruments will be automatically calculated previous to handing the data to the statistician:

- Substance Misuse History (CAGE) –Two scores will be calculated from 2x4 questions: 1) Positive for alcohol (y/n), and 2) Positive for drugs (y/n);
- Leverage - no total score but frequencies of those experiencing each type of leverage;
- MacArthur Admission Experience Survey (AES) –only total scores will be calculated for each of this instrument's subscales: 1) Perceived Coercion Scale; 2) Negative Pressures Scale, and 3) Procedural Justice Scale;

- Index of fairness;
- Index of effectiveness;
- Insight and Treatment Attitudes Questionnaire (ITAQ);
- Scale to Assess Therapeutic Relationship in Community Mental Health Care – Participants version (STAR –P) total score –and three subscale scores: 1) Positive Collaborations, 2) Positive Clinician Input, and 3) Non Supportive Clinician Input;
- Autonomy Preference Index (API) – only total scores will be calculated for the two subscales 1) Decision-making scale, and 2) Information Seeking Scale;
- Client Satisfaction Questionnaire (CSQ-8);
- Health Related Quality of Life Questionnaire (EQ-5D);
- Drug Attitude Inventory (DAI);
- Brief Psychiatric Rating Scale (BPRS);
- Global Assessment of Functioning (GAF).

Contact with service will be obtained by summing up questions 1-6 and 10 from the Client Service Receipt Inventory section of the CRF. The total number of contacts with carers of any profession will be calculated as well as the total number of phone and face-to-face contacts.

The following variables will be manually calculated previous to locking the dataset by comparing admission and discharge dates from (a) Index to 180 days; (b) 181 days to 365 days; (c) Index to 365 days:

- Number of nights to readmission;
- Total number of days in hospital;
- Total number of involuntary readmissions. A readmission will be considered involuntary if there is at least one change of status to “involuntary” between the admission and discharge dates;
- Total number of voluntary readmissions;
- Total number of CTO recalls.

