### **Primary analysis**

The primary outcome, psychiatric hospitalisation in the 12 month follow-up period, will be analysed using log-binomial regression adjusted for stratification factors (gender (male/female), schizophrenic status (yes/no), and duration of illness (< 2yrs,  $\geq$  2yrs)). Results will be presented as the relative risk of readmission under CTO compared to Section 17, with appropriate 95% confidence interval and 2-sided p-values.

If log-binomial modelling is not possible due to model instability then other alternatives will be explored such as Poisson regression with robust error variances, a method which has the advantage of presenting results as relative risks; or logistic regression with associated odds ratios.

The primary analysis will be conducted on the ITT population. There will be no adjustment for missing data as it is not expected that there will be any.

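### The mediation models add phone and face-to-face contact one at a time, so this exploratory analysis cannot separate the contributions of the two types of contact

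*SAP*

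**What the plan says.** The exploratory objective in SAP section 2 (Mediation analysis) concerns the effect on readmission of "process variables such as rate of contact and type of contact (i.e face-to-face vs. telephone contact". Section 5 (Derived and computed variables) builds the contact measures from the service receipt inventory: a total number of contacts, "as well as the total number of phone and face-to-face contacts".

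Section 13 (Mediator effects) names both aspects again: "The mediator effect of contact with service (rate of contact and type of contact) will be assessed for the primary outcome". It extends the analysis to three secondary outcomes: nights in hospital, nights to first readmission, and number of readmissions. The method is to refit the models already described for each outcome, "adding each contact with service variable independently as a fixed factor". For the primary outcome the base model is the one in section 8, where the outcome "will be analysed using log-binomial regression adjusted for stratification factors". The output is limited to one quantity: "Results will report the treatment effect after this adjustment, together with 95% confidence intervals whenever possible".

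**The concern.** The question sets one type of contact against the other, but the method as written never puts the two in the same model. No ratio, share or contrast of the two is planned either.

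Patients who are seen more often may also be phoned more often. If so, each count stands in partly for the other. A drop in the CTO effect after adjusting for phone contact could then come from face-to-face contact that the model leaves out, or the other way round if phone contact is the type that acts. A reader of the results would see two separate shifts in the treatment effect and might take each as the part carried by that type. This is the only planned analysis of how CTOs might work through contact, so the explanation offered for any effect could name the wrong component.

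**Working it through.** The SAP states no figure on this point, so there is none to reproduce. The check asks how far single-variable adjustment can mislead, and under which conditions.

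**Inputs, all assumed, because the SAP gives neither the correlation between the counts nor the difference in contact by arm.** F is face-to-face and P is phone contact, each with within-arm SD 1 and within-arm correlation ρ. CTO raises F by a_F = 0.5 and P by a_P = 0.5 or 0. Only F acts on readmission, with log relative risk (RR) b = −0.25 per SD.

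**Formulas on the log RR scale**
- Total CTO effect: b·a_F = −0.25 × 0.5 = −0.125, RR = exp(−0.125) = 0.88.
- Within arm, the expected F given P moves by ρ per unit of P. The CTO effect after adding P alone is therefore b·(a_F − ρ·a_P).
- Apparent share for the inert type P: 1 − (a_F − ρ·a_P)/a_F = ρ·a_P/a_F.

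With equal shifts the share is ρ. With a_P = 0 it is 0 whatever ρ is. For example, at ρ = 0.6: −0.25 × (0.5 − 0.6 × 0.5) = −0.05, RR = 0.95, share 60%.

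**Simulation check** (1,000,000 patients per row, RR from Poisson regression, a_F = a_P = 0.5; share = 1 − log adjusted RR / log total RR):

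| ρ | Total RR | RR after F alone | RR after P alone | Share for P, simulated | Share for P, formula | RR after F and P |
|---|---|---|---|---|---|---|
| −0.3 | 0.884 | 1.002 | 0.851 | −30% | −30% | 1.002 |
| 0 | 0.882 | 0.998 | 0.882 | 1% | 0% | 0.999 |
| 0.3 | 0.881 | 0.999 | 0.915 | 30% | 30% | 0.999 |
| 0.6 | 0.881 | 0.998 | 0.951 | 60% | 60% | 0.999 |
| 0.8 | 0.878 | 0.995 | 0.970 | 77% | 80% | 0.995 |

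With a_P = 0 the simulated share for P was 0% at every correlation. With both counts in one model, the RR for phone contact was 0.997 to 1.000 across all scenarios, which is the correct null.

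**What the planned output would look like.** At ρ = 0.6, F alone appears to explain 99% of the effect and P alone 60%. Together that is 159%. The two shifts overlap, and nothing in the planned output shows which is real.

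**Size against sampling error.** Take 165 per arm (half the randomisation target of 330) and an assumed readmission risk of 0.40. The standard error of the log RR is about √(2 × 0.6 / (165 × 0.4)) = 0.135. Around an RR of 0.88 the 95% interval is exp(−0.125 ± 1.96 × 0.135), about 0.68 to 1.15. At ρ = 0.5 the misattribution moves the point estimate from 0.88 to exp(−0.0625) = 0.94, well inside that interval.

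**Cost of a joint model.** Intervals for the contact coefficients widen by about 1/√(1 − ρ²). At ρ = 0.7 this is 1/√(1 − 0.49) = 1.40.

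**The case against.** A reader might infer that phone contact will take the credit for face-to-face contact, and the reverse. The SAP does not support that. The error needs a correlation between the counts within arm and an arm shift in the variable added, and the SAP gives neither. With either absent there is no error in the CTO effect, and with negative correlation the error runs the other way. The reverse case also needs phone contact to have an effect of its own. In the scenarios above, adding face-to-face contact alone gave the right answer, because phone contact was made inert.

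A reader might also infer that the analysis cannot address type of contact at all. That goes too far. The single-variable models still show how far the CTO effect moves with each type. What they cannot give is the distinct contribution of each.

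The joint model does well here partly by construction. If calls lead to visits, adjusting for both blocks part of the pathway through phone contact, and the single-variable model is then a legitimate summary. Single-variable models are also reasonable for the rate of contact. Both are reasons to keep them, and neither is a reason to leave out a joint model.

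The word *independently* might mean separate terms in one model. One at a time is the natural reading, and on the other reading total contact could be collinear with its parts. The sentence needs clarifying either way.

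Finally, section 13 is headed "13. Analysis of exploratory objectives", and the shift at issue is small beside the sampling error. Both points stand and limit the weight.

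**Conclusion.** The concern holds as a limitation of an exploratory analysis. As written, no planned model contains both phone and face-to-face contact, so the contributions of the two types cannot be separated, although section 2 asks about type.

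Misattribution is possible but not established. With equal arm shifts and one active type, the share wrongly given to the inert type is roughly the within-arm correlation. These sizes rest on assumed effects, a log-linear risk and no unmeasured confounding between contact and readmission. They carry over only loosely to time to first readmission, where a change in a hazard ratio after adjustment is not a clean decomposition.

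The primary and secondary treatment comparisons are untouched. Low weight.

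**What to change.** In SAP section 13, Mediator effects:

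- State that each contact variable is first added in its own model. Keep these models, with total contact addressing rate and each type alone as descriptive.
- Add, for each outcome, one model with the phone and face-to-face counts entered together. Leave total contact out of it if the total is the sum of the two, which section 5 does not say and should make clear.
- Report the treatment effect from the joint model beside the single-variable results, with the adjusted association and 95% confidence interval for each type.
- State that the shifts from the single-type models will not be read as distinct or additive mediated shares.

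The cost is SAP wording and four more models (one primary and three secondary outcomes), from variables already derived, plus the wider intervals for the contact coefficients shown above. The joint model does not remove confounding, since contact is measured after randomisation, so the results remain exploratory.

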#### **4. *Data collection***

All primary outcome data were collected from medical records. Client Service Receipt Inventory was initiated from interview with patients but confirmed from case note examination. Notes from other hospitals and from the criminal justice system will be pursued when applicable.

A range of the secondary measures rely on patient interviews which are administered by the research assistants by reading out the questions contained in booklets specially designed for the RCT and recording the patient's reply. These booklets contain detailed assessment of demographics, clinical history, prior MHA use and criminal justice system contacts. They also record the assessment date, patient ID, interviewer ID, and time point. Current status will be assessed using the following well validated and widely used structured questionnaires:

- Mac Arthur Admission Experience Survey (AES)
- Index of fairness
- Index of effectiveness
- Psychiatry Autonomy Preference Index (API)
- Insight and Treatment Attitudes Questionnaire (ITAQ)
- Scale To Assess Therapeutic Relationships -Participant Version (STAR-P)
- Client Satisfaction Questionnaire (CSQ-8)
- Health Related Quality of Life (EQ-5D)
- Client Service Receipt Inventory (CSRI)
- Drug Attitude Inventory (DAI-10)
- Brief Psychiatric Rating Scale (BPRS-24)
- Global Assessment of Functioning (GAF)
- Substance Misuse History (CAGE).

The following non-validated instruments were also recorded:

- Experience of specific types of leverage;
- Patient Capabilities Questionnaire (PCQ), Quality of Life, which was applied in order to investigate its validity within the health economy analysis (not within the scope of this SAP);
- In addition, new items recording ‘Types of pressure’ in relation to experience of Leverage were included;
- A very small response rate is expected in the following validated questionnaire: Scale to Assess Therapeutic Relationships – Clinicians Version (STAR-C). It will be excluded from the analysis;
- The carer questionnaires will also be excluded from analysis as the patients in general did not have carers, and among those who had there was a low response rate ending up with only 30 questionnaires completed.

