### **Secondary analysis**

Secondary analyses will be conducted using the ITT population. No adjustment for missing data will be performed when analysing these outcomes as no missing data is expected for them.

Secondary outcomes will be analysed in the same way as primary outcomes using multiple regression models with adjustment for stratification factors. The type of regression model will depend on the data distribution. All model assumptions will be assessed.

Number of readmissions and number of nights in psychiatric hospitalization are count outcomes and will be analysed using Poisson or negative-binomial regression models depending on data dispersion. Results will be presented as incident-density ratios, which are interpreted in the same way as relative risks.

The number of nights to first readmission from INDEX to 365 days, and time under compulsion, are time to event outcomes and analyses will be performed using proportional hazards regression, with results presented as hazard ratios with 95% confidence intervals. Kaplan Meier plots will also be presented and the median time to readmission calculated with 95% confidence intervals.

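### The exploratory mediation models adjust for service contact with only the three stratification factors as baseline covariates, so the contact-adjusted CTO effect can be confounded

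*SAP*

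**What the plan says.** Section 13 of the SAP, under Mediator effects, covers the primary outcome and three secondary outcomes: nights in hospital, nights to first readmission and number of readmissions. The analysis consists of "fitting the same models as described for the primary outcome and secondary outcomes", "adding each contact with service variable independently as a fixed factor". The output is stated as "Results will report the treatment effect after this adjustment", with confidence intervals where possible. The purpose is explanatory: "This analysis aims to explain how the difference of treatment between the two groups occurred based on the contact with service experienced".

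The models carried over are set in sections 8 and 9. The primary outcome "will be analysed using log-binomial regression adjusted for stratification factors", namely gender, schizophrenic status and duration of illness. The secondary outcomes are analysed "using multiple regression models with adjustment for stratification factors". No further baseline covariate enters when contact is added.

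The contact variable is defined in section 5, Derived and computed variables: "Contact with service will be obtained by summing up questions 1-6 and 10 from the Client Service Receipt Inventory section of the CRF", with phone and face-to-face totals as well.

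Other prognostic baseline data are available. Section 4 says of the interview booklets: "These booklets contain detailed assessment of demographics, clinical history, prior MHA use and criminal justice system contacts". Section 6 lists baseline BPRS-24, GAF, legal history and type of care provider for tabulation. Section 5 names BPRS, GAF and type of service as subgroup variables for the readmission outcomes.

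**The concern.** Randomisation balances the arms. It does not balance patients who end up with the same amount of contact. Suppose CTO raises contact and sicker patients are also seen more often. A leave patient with a given contact level then tends to be sicker than a CTO patient with that level. Comparing arms at equal contact compares patients of unequal severity, and the arm coefficient absorbs the difference. This is mediator-outcome confounding. It would remain even if contact were counted and timed perfectly.

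At stake is the explanation the analysis is meant to supply. A confounded coefficient could be reported as an effect of CTO that does not run through contact when there is none, or could misstate a real one. The section states no assumption about this confounding and plans no sensitivity analysis for it.

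A second, narrower issue concerns scale. Nights to first readmission is analysed by hazard ratio. A hazard ratio for arm can change when any strong predictor is added, including one that CTO does not affect, so a change in it is not by itself evidence of mediation.

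**Working it through.** The mediation section states no figure, so there is none to reproduce. The check asks what the planned model returns when the true answer is known to be nil.

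**Inputs from the SAP.** Allocation is 1:1 and the recruitment target is 330 (section 3). Arm and the three stratification factors are in the model (sections 8 and 9). Robust Poisson is a named fallback (section 8).

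**Assumed inputs, not in the SAP.**
- *a*: shift in contact caused by CTO, in SD.
- *ρ*: correlation of an omitted baseline factor U (for example severity) with contact within arm.
- RR_U: risk ratio of readmission per SD of U.
- Arm and contact have no effect on readmission (true RR = 1).

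**Formula.** Write contact as M = a·T + ρ·U + error, with T the arm (1 = CTO), U standard normal and within-arm variance of M equal to 1. Let log risk = constant + log(RR_U)·U. Given M and T, the mean of U is ρ(M − a·T). The arm coefficient after adjusting for contact is therefore −a·ρ·log(RR_U), so

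false RR = RR_U^(−a·ρ).

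**Check against simulation.** N = 330, 1,000 runs per scenario, mean risk about 36%, robust Poisson with the stratification factors:

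| a | ρ | RR_U | Formula | Simulated RR | False-positive rate |
|---|---|---|---|---|---|
| 0.3 | 0.5 | 1.5 | 0.94 | 0.94 | 7.6% |
| 0.5 | 0.3 | 1.3 | 0.96 | 0.96 | 6.5% |
| 0.5 | 0.5 | 1.5 | 0.90 | 0.91 | 9.4% |
| 1 | 0.3 | 1.3 | 0.92 | 0.93 | 7.2% |
| 1 | 0.5 | 1.5 | 0.82 | 0.82 | 24.5% |
| 1 | 0.6 | 1.6 | 0.75 | 0.76 | 41.4% |

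In every row the model without contact gives RR 1.00 to within 0.01. Adding U to the contact model returns 0.99-1.01, with false-positive rates of about 4-7%. At 100,000 patients the bias persists (0.91 for a = 0.5 and 0.81 for a = 1, both with ρ = 0.5 and RR_U = 1.5), so it is not small-sample noise.

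**When it vanishes.**
- CTO does not change contact (a = 0): RR 1.01.
- U does not drive contact: RR 1.00.
- U does not drive readmission: RR 1.00.
- The shared driver is itself a stratification factor: the planned model gives 1.00 and 0.99. Leaving that factor out would give 0.92 and 0.85.

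**Range used for the conclusion.** Take ρ = 0.6, a from 0.25 to 0.75 and RR_U from 1.5 to 1.8.
- Formula: 1.5^(−0.15) = 0.94 to 1.8^(−0.45) = 0.77.
- Simulation with readmission about 45% and risks kept below 1: about 0.95 to 0.79.
- With the sign of ρ reversed (sicker patients seen less): 1.06 to 1.30 by formula, about 1.06 to 1.28 by simulation.

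**What an imperfect covariate achieves.** If the measured covariate correlates r with U, the share of bias left is (1 − r²)/(1 − ρ²r²). With r = ρ = 0.6 this is 0.64/0.8704 = 0.74, so 26% is removed. Simulations give about a quarter to a third.

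**Hazard ratio.** Cox models were fitted with a predictor that CTO does not affect, with a hazard ratio of 2 per SD. Adding it moved the arm hazard ratio from 0.61-0.65 to 0.59-0.61, depending on the event rate (for example 0.64 to 0.60). No mediation was present.

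**The case against.** Several points on the other side stand.

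- **Some baseline adjustment is present.** A reader might infer that the mediation models contain no baseline covariate. They do not: three stratification factors are carried over, and confounding through those is removed.
- **The bias is conditional.** A reader might infer that a false effect appears even if CTO does nothing at all. It does not. CTO must change contact, and an omitted factor must drive both contact and readmission. The SAP documents neither path. A CTO effect on contact is, however, the premise of any mediation analysis, so the problem arises where the analysis is of interest.
- **The direction is not known.** A reader might expect false protection. Sicker patients may disengage and be seen less, and then the bias goes the other way.
- **The size is uncertain beside sampling error.** At N = 330 and 36% risk, the SE of log RR is √(2 × 0.64/(0.36 × 165)) = 0.147. An estimate of 0.91 would carry a 95% interval of about 0.68 to 1.21.
- **The proposed covariates are proxies.** RR returns to 1.00 in simulation because the true driver is added. BPRS and GAF may recover only part. Type of service has seven categories and could strain a log-binomial fit.
- **The hazard-ratio issue is limited.** The SAP does not say in terms that mediation will be read from a change in ratio, though its aim implies the comparison. It touches one of four outcomes, plus the primary outcome if the logistic fallback is used.
- **The analysis is exploratory.** It also cites a methods reference that is not at hand.

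None of this supplies the missing covariates. It sets the limits of the claim.

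**Conclusion.** The point holds in conditional form. The planned contact-adjusted CTO effect is biased if CTO changes contact and a baseline factor outside the three stratification factors drives both contact and readmission. Under the stated assumptions (shift 0.25-0.75 SD, correlation 0.6, RR 1.5-1.8 per SD), a true RR of 1 would appear as about 0.95-0.79, or about 1.06-1.28 with the opposite sign for contact. These figures illustrate what is possible and do not estimate the bias in this trial.

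The documents do not support extending this to the main results. The primary intention-to-treat comparison does not condition on contact and is unaffected. The issue is an avoidable weakness in one exploratory analysis that is given an explanatory purpose.

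**What to change.** In section 13, Mediator effects:

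1. Add baseline BPRS, GAF, prior Mental Health Act use and type of service to each model. Collapse sparse service categories, and use the robust Poisson fallback from section 8 if the log-binomial model is unstable.
2. Fit each model with and without contact on the same patients. Contact comes from the CSRI, which the SAP classes as a tertiary outcome, and it expects self-reported tertiary outcomes to have missing values.
3. State that these covariates reduce mediator-outcome confounding but may not remove it, and label the result exploratory.
4. For nights to first readmission, and for the primary outcome if logistic regression is used, do not read mediation from the change in hazard or odds ratio alone. Compare on a risk or mean scale. An indirect effect with a bootstrap interval is one way to do this, but not the only one.

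The cost is a few lines of SAP text and modest programming on data already collected. The price is some loss of model stability from the extra covariates, and residual confounding that must still be acknowledged.

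### The mediation analysis reports only the contact-adjusted treatment effect, so the mediated part has no interval, and its hazard ratio can shift without mediation when contact strongly predicts readmission

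*SAP*

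**What the plan says.** Section 2 lists mediation through service contact as an exploratory objective. Section 13 (Mediator effects) gives the purpose: "This analysis aims to explain how the difference of treatment between the two groups occurred based on the contact with service experienced". The method is to refit the primary and secondary outcome models, "adding each contact with service variable independently as a fixed factor". The output rule is: "Results will report the treatment effect after this adjustment, together with 95% confidence intervals whenever possible".

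Four outcomes are covered: readmission yes/no, nights in hospital, and "2) number of nights to first readmission; and 3) number of readmissions, from INDEX to 365 days". Each inherits its model from an earlier section:

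- **Readmission** (Section 8) "will be analysed using log-binomial regression adjusted for stratification factors". If that model is unstable, the alternatives are robust Poisson regression "or logistic regression with associated odds ratios".
- **Nights in hospital and number of readmissions** (Section 9) use Poisson or negative binomial regression.
- **Nights to first readmission** (Section 9): "analyses will be performed using proportional hazards regression, with results presented as hazard ratios with 95% confidence intervals".

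Two other places bear on the point. Section 5 (Derived and computed variables) builds contact with service from items of the Client Service Receipt Inventory (CSRI). Section 10 (Tertiary analysis) places CSRI service usage among the outcomes to be compared by linear regression. No section defines an indirect effect, gives an interval or test for the change on adjustment, or adds covariates that predict both contact and readmission beyond the stratification factors.

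**The concern.** To explain a treatment difference through contact, one needs an estimate of what passed through contact and a measure of its uncertainty. The planned output is the complement of that: the effect remaining at fixed contact. The total effect is reported in Sections 8 and 9, so the two can be set side by side. But they come from the same patients and are highly correlated, so their separate intervals say little about how well the difference between them is known.

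A second difficulty concerns the scale. Under the planned log-link models, adding a covariate that does not differ by arm leaves the relative risk or rate ratio essentially where it was. A hazard ratio or an odds ratio can move, because neither is collapsible. For nights to first readmission, and for the binary outcome under the logistic fallback, a change on adjustment therefore mixes mediation with a purely arithmetical shift. At stake is the reading of one stated exploratory objective.

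**Working it through.** The SAP gives no figure for the mediation analysis, so there is nothing to reproduce. Two sizes come from it: 288 patients (Section 3, Sample size determination) and the randomisation target of 330 (Section 3, Overall study design and plan). It gives no control readmission rate, contact effect or confounding strength, so these are assumptions. A control risk of 0.48 fits the stated size: a 16-point difference at two-sided 5% and 80% power without continuity correction needs 288 at 0.46 vs 0.30 and 292 at 0.48 vs 0.32.

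**1. Size of the change against the reported interval (relative risk).** Assume 144 per arm, control risk 0.48, high contact in 40% of controls and 70% of the CTO arm, log RR −0.5 for high contact, and a direct RR of √(0.32/0.48) = 0.816.

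- Expected change in log RR = ln[(0.3 + 0.7e^−0.5)/(0.6 + 0.4e^−0.5)] = ln(0.725/0.843) = −0.151.
- Over 1,000 simulated trials (robust Poisson), RR moved from 0.70 to 0.81. The mean log change was 0.155, with SD 0.054 across trials. With contact equal by arm, the mean change was 0.001 (SD 0.028).
- SE of the total log RR = √[(1 − 0.48)/(144 × 0.48) + (1 − 0.335)/(144 × 0.335)] ≈ 0.146; half-width 1.96 × 0.146 ≈ 0.29.
- The change is 0.155/0.054 ≈ 2.9 of its own SDs, but only 0.155/0.29 ≈ 0.5 of that half-width. An interval for the change would be about 0.155 ± 1.96 × 0.054, or 0.05 to 0.26.
- The expected change does not depend on the control risk. At the same RR, the half-width is about 0.40 at control risk 0.30 and 0.20 at 0.70, so the change stays inside it over that range.

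A second set of simulations used 165 per arm, readmission risk about 0.40, CTO raising contact by 0.4 to 0.5 SD, and contact log RR −0.2 to −0.3 per SD. A 95% interval for the indirect effect excluded zero in 77% to 98% of trials, and in 5% when CTO did not affect contact. The total and adjusted intervals were never disjoint.

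**2. Hazard ratio with nothing mediated.** Contact is unrelated to arm but predicts readmission.

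| Conditional HR | Contact effect per SD | HR without contact | HR with contact | Change in log HR |
|---|---|---|---|---|
| 0.70 | HR 0.75 | 0.701 | 0.696 | 0.007 (2%) |
| 0.70 | HR 0.5 | 0.726 | 0.699 | 0.038 (12%) |
| 0.70 | HR 0.37 | 0.750 | 0.694 | 0.078 (27%) |
| 0.60 | log HR 0.5 | 0.623 | 0.600 | 0.038 (8%) |
| 0.60 | log HR 1.0 | 0.670 | 0.604 | 0.104 (26%) |
| 1.00 | log HR 1.0 | 0.998 | 0.999 | none |

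Percentages are of the unadjusted log HR; for example (ln 0.726 − ln 0.699)/|ln 0.726| = 0.038/0.320 = 12%. The movement is away from 1, so it works against the attenuation that real mediation would produce.

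**3. Other scales, nothing mediated (400,000 simulated patients).** For a binary contact variable with readmission RR 1.5 or 2.5, the treatment RR went from 0.672 to 0.672 and from 0.664 to 0.665. The odds ratio went from 0.516 to 0.506 and from 0.506 to 0.460.

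**4. Confounding of contact and readmission.** With an unmeasured common cause and no effect of contact on readmission, RR still moved from 0.67 to 0.63 on adjustment for contact.

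**The case against.** Much can be said for the plan as written. It already supplies most of the ingredients: the total effect (Sections 8 and 9), a regression comparison of CSRI service usage between arms (Section 10), and the adjusted effect (Section 13). If contact did not differ by arm, Section 10 should show it, and a careful reader would not take a shift in the hazard ratio for mediation. For three of the four outcomes under the planned models, the change can be read by subtracting logs. In the first simulation, attenuation from 0.70 to 0.81 is visible in the planned output. All of this stands.

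A reader might infer that mediation could not be shown at all, or that the analysis would nearly always look negative. The document does not support that. It states no rule based on overlapping intervals and no criterion for declaring mediation. What is missing is an interval for the change.

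A reader might also infer that the hazard ratio will shift in general. It does so only with a non-null treatment effect and a strongly prognostic contact variable. The contact effects in the second set of simulations (RR e^−0.3 to e^−0.2, about 0.74 to 0.82 per SD) are near the hazard ratio of 0.75 at which the shift is only 2%. With about 330 × 0.40 = 132 events, the SE of a log HR is √(4/132) ≈ 0.17, so shifts of 0.04 and 0.08 are under half a standard error.

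Finally, the analysis is exploratory, Section 13 cites a methods reference that is not at hand, and an indirect effect with a bootstrap interval would look precise while still being open to confounding. That last caution has to be built into any fix.

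**Conclusion.** The point holds in a limited form. The output rule in Section 13 does not match its stated purpose: it gives the residual effect with an interval, and leaves the mediated part to informal subtraction without one. Under the assumptions above, a change of about 2.9 of its own SDs occupies only half the half-width of the total effect's interval.

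For nights to first readmission, and for the binary outcome under a logistic fallback, even the informal subtraction can mislead. With contact hazard ratios of 0.5 or 0.37 per SD and a true conditional hazard ratio of 0.70, the log hazard ratio moves by 12% or 27% with nothing mediated. At 0.75 per SD the movement is about 2%, and with no treatment effect there is none. These magnitudes rest on assumed event rates and contact effects; the SAP supplies neither.

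The consequence is confined to an exploratory objective. The primary and secondary treatment comparisons are untouched.

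**What to change.** Rewrite the output rule in Section 13 (Mediator effects):

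- For each outcome, combine an arm-to-contact model (Section 10 already plans one for CSRI service usage) with the contact-adjusted outcome model. Add baseline variables that predict both contact and readmission.
- Report the indirect and direct effects beside the total effect, with bootstrap 95% confidence intervals for the indirect and direct effects.
- For nights to first readmission, and for the binary outcome if logistic regression is used, express the effects on a collapsible scale: the 365-day readmission probability or mean readmission-free nights to day 365. State that a before-and-after change in a hazard or odds ratio will not be read as mediation.
- State that the indirect effect assumes no unmeasured confounding of contact and readmission.

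No new data are needed. The cost is a few sentences and modest programming, which grows if CSRI contact data are missing and the bootstrap must be combined with the multiple imputation planned in Section 5.
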